3.2 Number of Patients and Study Participation

3.2.1 Number of Patients

The number of patients in Dose-Determination Phase Segment 1 will depend on the number of dose cohorts assessed and the DLTs observed (6 to 9 patients per cohort).

Approximately 20 patients will be enrolled in Dose-Determination Phase Segment 2 to achieve 16 DLT-evaluable patients (Arm A: 12 patients, Arm B: 4 patients).

Approximately 40 patients will be enrolled in the Expansion Phase (20 patients in each cohort).

3.3 Definitions: End of Treatment, End of Study, and Study Duration

3.3.1 End of Treatment

The end of treatment is defined as the date on which the patient received his last treatment with either CORT125281 or enzalutamide, whichever is later.

3.3.2 End of Study

In accordance with European Union (EU) and US Food and Drug Administration (FDA) regulations, the end of study is defined as the date of last contact (by visit, telephone, or email) with any study patient. The Sponsor will ensure that the Institutional Review Board/Independent Ethics Committee (IRB/IEC) and the regulatory authority are notified that the study has finished according to Sponsor's Standard Operating Procedures (SOPs) and/or local or national regulations.

3.3.3 Study Duration

Patients will receive CORT125281 in combination with enzalutamide until reaching a protocol-defined event of disease progression, experiencing unmanageable toxicity, or until other treatment discontinuation criteria are met (Section 4.4.1). As per PCWG3, patients with an isolated PSA rise after an initial decline who show evidence of benefit should continue treatment until radiographic or clinical progression.

All patients will be followed for progression, information on subsequent anticancer therapies (start and end date and response) and survival.

3.4 Study Termination by Sponsor

If the Sponsor, Investigator, Study Monitor, or regulatory officials discover conditions arising during the study that indicate that the study should be halted or that the study site's participation should be terminated, this action may be taken after appropriate consultation between the Sponsor and Investigator. Conditions that may warrant termination of the study include, but are not limited to, the following:

- Discovery of an unexpected, serious, or unacceptable risk to the patients enrolled in the study
- Decision on the part of the Sponsor to suspend or discontinue testing, evaluation, or development of the product

Study termination and follow-up will be performed in compliance with applicable regulations.

4 STUDY POPULATION

The following eligibility criteria are designed to select patients with mCRPC (prostate cancer that is resistant to medical or surgical treatments that lower testosterone) and patients with mCRPC with rising PSA, defined as a 25% increase over nadir and an absolute value >1 ng/mL, based on 2 measurements at least 1 week apart, for whom the protocol treatment is considered appropriate. All relevant medical and nonmedical conditions will be taken into consideration when deciding whether this protocol is suitable for a particular patient.

4.1 Inclusion Criteria

Each patient must meet the following criteria to be enrolled in this study:

1. Able to understand the purpose and risks of the study; willing and able to adhere to scheduled visits, treatment plans, laboratory tests, and other study evaluations and procedures, and provide written informed consent.
2. Males ≥ 18 years of age at time of signing consent.
3. Histologically confirmed adenocarcinoma of the prostate with metastatic disease.
4. Dose-Determination Phase Segment 1 and Expansion Phase: Progressive disease as defined by PSA or imaging after most recent prior therapy. PSA ≥ 1 ng/mL, if a confirmed rise in PSA is the only indication of progression. Progression by PSA requires rising PSA over a previous reference value by at least 2 measurements obtained ≥ 1 week apart. PSA measurements can be collected during or after the most recent prior therapy.
5. Dose-Determination Phase Segment 2: Currently receiving enzalutamide with a rising PSA as follows:
 - a. Rising PSA: 25% increase over nadir and an absolute value of >1 ng/mL by at least 2 measurements obtained ≥ 1 week apart. PSA measurements can be collected during or after the most recent prior therapy.
 - b. Patients must have received enzalutamide for a minimum of 12 weeks and be on stable doses of enzalutamide ≥ 80 mg QD for at least 4 weeks prior to Cycle 1 Day 1.
 - Patients will continue enzalutamide without interruption during the Screening Period (no wash-out period).
 - This will be the enzalutamide starting dose for combination with CORT125281 beginning on Cycle 1 Day 1.
 - c. M0 disease is allowed.
6. Expansion Phase: Patients must have progressed while receiving an androgen-directed therapy as follows:
 - a. Abi-Resistant Cohort: Patients must have progressed during treatment with abiraterone.
 - b. ARant-Resistant Cohort: Patients must have progressed during treatment with enzalutamide or second-generation AR-blocking therapies. Patients progressing on enzalutamide immediately prior to enrolling in this study must be on stable doses of enzalutamide. These patients will continue enzalutamide without interruption during the Screening Period (no wash-out period required).
7. Baseline tumor assessment performed within 28 days prior to the first dose of study treatment (CORT125281 and/or on-study enzalutamide, whichever is earlier).

8. Prior surgical or chemical castration with serum testosterone <1.7 nmol/L (50 ng/dL). If the method of castration is use of a luteinizing hormone-releasing hormone (LHRH) analogue, there must be a plan to maintain effective LHRH analogue treatment for the duration of the trial.
9. If bisphosphonates or denosumab were started within 4 weeks prior to first dose of CORT125281, then Grade 2 or greater toxicities were not observed.
10. Consent to provide paired tissue biopsies, obtained within 6 weeks prior to the first study dose of study treatment (CORT125281 and/or on-study enzalutamide, whichever is earlier) and at Cycle 2 Day 1 (Window of within 14 days prior to Cycle 2 Day 1 is acceptable. Soft tissue biopsy is preferred, when possible).
 - A sufficient number of patients will be enrolled to provide paired biopsies in approximately 4 patients enrolled per cohort in Dose-Determination Phase Segment 1, approximately 10 patients (total) in Dose-Determination Phase Segment 2, and approximately 10 patients per cohort in the Expansion Phase. For these patients, providing paired tissue biopsies is mandatory. Consent to provide biopsies will be optional in the remaining patients. The requirement for biopsies will be communicated to each patient during the enrollment process. Inability to obtain biopsy tissue will not impact the patient's ability to participate in the study.
 - Patients may also consent to provide on-study optional biopsies (1) obtained during procedures that are conducted as part of the patient's standard treatment; and/or (2) at the time of disease progression.
11. Consent to provide mandatory pharmacogenomic blood sample (Dose-Determination Phase Segment 1 only).
12. Eastern Cooperative Oncology Group (ECOG) performance status of 0 or 1.
13. Adequate baseline organ function within 14 days prior to the first dose of study treatment (on-study enzalutamide and/or CORT125281, whichever is earlier):
 - a. Absolute neutrophil count (ANC) $\geq 1,500/\mu\text{L}$, platelet count $\geq 100,000/\mu\text{L}$, and hemoglobin ≥ 9 g/dL (NOTE: patients may not have received any growth factors or blood transfusions within 7 days prior to the hematologic laboratory values obtained during the Screening Period)
 - b. Total bilirubin $\leq 1 \times$ the upper limit of normal (ULN), and alanine aminotransferase (ALT) and aspartate aminotransferase (AST) $\leq 3 \times$ ULN. Patients with Gilbert's syndrome may have bilirubin $>1.5 \times$ ULN if there is no evidence of hepatobiliary obstruction or hepatic dysfunction
 - c. Creatinine \leq ULN (National Cancer Institute Common Terminology for Adverse Events [NCI-CTCAE] Grade 0); if creatinine $>$ ULN: creatinine clearance >60 mL/min/1.73 m² according to the Modification of Diet in Renal Disease (MDRD) Study equation ([Levey et al. 1989](#))
 - d. Albumin ≥ 3.0 g/dL (≥ 30 g/L)
 - e. Activated partial thromboplastin time (aPTT) must be $\leq 1.5 \times$ ULN and international normalized ratio (INR) <1.5 . Patients on anticoagulant therapy will have an appropriate aPTT and INR as determined by the Investigator
14. Patients receiving systemic corticosteroids greater than 2 weeks in duration within 3 months of study entry or with clinical evidence of adrenal insufficiency must have adequate adrenal function as evidenced by a morning plasma cortisol concentration of

greater than or equal to 10 µg/dL or a plasma cortisol response to an ACTH (cosyntropin) stimulation test that is deemed clinically normal (value of greater than 18 µg/dL).

15. If a patient engages in sexual intercourse with a woman of childbearing potential, a condom with spermicide and another form of birth control must be used during and for 100 days after the final dose of study treatment (CORT125281 or enzalutamide, whichever is later). Acceptable methods of birth control (to be used in conjunction with a condom and spermicide) are:
 - a. Established use of oral, injected or implanted hormonal methods of contraception
 - b. Placement of an intrauterine device or intrauterine system
 - c. Barrier methods of contraception: occlusive cap (diaphragm or cervical/vault caps) with spermicidal foam/gel/film/cream/suppository
 - d. Tubal ligation
 - e. Vasectomy or other surgical castration prior to initial Screening

A condom is required during and for 100 days after completing treatment with enzalutamide if a patient is engaged in sexual activity with a pregnant woman. Patients must also agree to avoid sperm donation during the study and for at least 100 days after the final treatment administration.

16. Able to swallow and retain oral medication without uncontrolled nausea or emesis.

4.2 Exclusion Criteria

Patients who meet any of the following criteria will not be permitted entry to the study:

1. Received chemotherapy, non-palliative radiotherapy, immunotherapy, or any investigational cancer therapies within 21 days prior to the first dose of CORT125281, or treatment with such therapies is planned during protocol treatment. Concomitant anticancer therapy is not permitted during the enzalutamide Lead-In Period during Dose-Determination Phase Segment 1.
2. More than 2 prior cytotoxic chemotherapy regimens for the treatment of mCRPC.
3. The Dose-Determination and Expansion Phases will exclude patients for the following:
 - Dose-Determination Phase (Segment 1 only):
 - Progressed during treatment with enzalutamide prior to Cycle 1 Day -28 (only applies to patients receiving enzalutamide lead-in) or
 - Received prior second-generation anti-androgen and require urgent disease response or stabilization
 - Expansion Phase, Abi-Resistant Cohort:
 - Received prior therapy with enzalutamide or
 - Received prior second-generation anti-androgen and require urgent disease response or stabilization
 - Expansion Phase, ARant-Resistant Cohort: Require urgent disease response or stabilization
4. Ongoing or anticipated therapy with hormone therapy (other than LHRH analogue), including any dose of megestrol acetate (Megace), finasteride (Proscar), dutasteride (Avodart) or received abiraterone within 28 days prior to the first dose of CORT125281.

5. Received palliative radiotherapy within 2 weeks prior to the first dose of study treatment (on-study enzalutamide and/or CORT125281, whichever is earlier). If palliative radiation therapy included the pelvis, a minimum of 4 weeks is required between palliative radiotherapy and the first dose of CORT125281.
6. Contraindication or precaution for enzalutamide including history or risk factors for seizures; fructose intolerance; PRES, or discontinuation of prior treatment with enzalutamide due to toxicity.
7. Parenchymal brain metastases.
8. Any clinically significant uncontrolled condition that may increase the risk to the study patient or that the Investigator considers places the patient at unacceptable risk, including but not limited to the following:
 - a. Myocardial infarction resulting from acute coronary syndrome or transient ischemic attack with 12 months of enrollment
 - b. Acute coronary syndromes (including unstable angina), coronary angioplasty, stenting, or bypass grafting within the past 6 months prior to enrollment, Class III or IV heart failure as defined by the New York Heart Association functional classification
 - c. Recent history of or risk factors for torsades de pointes, including marked baseline prolongation of QT interval (eg, repeated demonstration of a corrected QT [QTc] interval >450 milliseconds using Fridericia's formula [QTcF] or need for concomitant medication associated with QT prolongation; refer to <https://www.crediblemeds.org/>)
 - d. Uncontrolled hypertension: Sustained systolic blood pressure ≥ 180 mmHg or diastolic blood pressure ≥ 100 mmHg; patients will be considered eligible if hypertension is treated and controlled during Screening
 - e. Active infection requiring IV anti-infective treatment
 - f. Human immunodeficiency virus (HIV) or current chronic/active infection with hepatitis C virus or hepatitis B virus, including:
 - i. Patients with chronic or active hepatitis B as diagnosed by serologic tests are excluded from the study. In equivocal cases, hepatitis B or C polymerase chain reaction may be performed and must be negative for enrollment.
 - g. Active autoimmune disease requiring systemic treatment
 - h. Alcohol or other substance abuse or cirrhosis
9. Received herbal products or alternative therapies that may decrease PSA levels or that may have hormonal anti-prostate cancer activity (eg, saw palmetto, PC-SPES, PC-HOPE, St. John's wort, selenium supplements, grape seed extract) within 21 days of study treatment initiation or plans to initiate treatment with these products/alternative therapies during the entire duration of the study.
10. Received systemic GCs within 21 days prior to the first dose of CORT125281, or requirement for chronic or frequently used systemic or inhaled GCs for medical conditions (eg, rheumatoid arthritis, immunosuppression after organ transplantation). Short courses (≤ 5 days) for non-cancer-related reasons are allowed if clinically required (such as prophylaxis for CT).
11. Concurrent therapy with strong inhibitors or inducers of CYP3A4 or CYP2C8 or with sensitive substrates of CYP3A4, CYP2C9, or CYP2C19. For patients currently receiving strong CYP3A4 or CYP2C8 inducers, a minimum wash-out period of 21 days

is required prior to initiating the first day of CORT125281. For patients currently receiving strong CYP3A4 or CYP2C8 inhibitors, a minimum wash-out period of 14 days is required prior to initiating the first dose of CORT125281. Prohibited medications are not permitted during the enzalutamide Lead-In Period during Dose-Determination Phase Segment 1, as per protocol Section 5.9.2.

- Co-administration of enzalutamide with warfarin will not be exclusionary. If co-administration of warfarin cannot be avoided, conduct additional INR monitoring
- Refer to [Appendix C](#) for examples of prohibited concomitant medications and foods

12. Toxicities of prior therapies (except alopecia) that have not resolved to NCI-CTCAE of Grade 1 or less.
13. Any other concurrent cancer or a history of another invasive malignancy within the last 3 years that has a likelihood of recurrence of >30% within the next 5 years. Adequately treated non-melanoma skin cancers or non-muscle invasive urothelial cancer or other tumors curatively treated with no evidence of disease are permissible.
14. Concurrent treatment on other Phase 1, 2, or 3 investigational treatment studies for the treatment of prostate cancer.

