Dose Level	Resulting CORT125281 Dosage (QD)		Open-Label Bottle (CORT125281)	Blind-Label Bottle (CORT125281 or Placebo) ^a
	Arm A	Arm B		
1 (Starting Dose)	240 mg	240 mg	6 capsules	0 capsules
+1 (First Increase)	280 mg	240 mg	6 capsules	1 capsule
+2 (Second Increase)	320 mg	240 mg	6 capsules	2 capsules

QD, once daily.

Note: The CORT125281 dosage will be escalated in 2-week intervals unless there are intolerable Grade 2 toxicities, dose-limiting toxicities, or Grade 3 or greater toxicities attributed to CORT125281 (Section 5.7).

^a Note: The blind-label bottle contains blinded capsules (CORT125281 [Arm A] or placebo [Arm B]).

During the double-blind portion of the Dose-Determination Phase (ie, Segment 2), an unblinded Medical Monitor independent of the study team will provide additional oversight for the study, including review of serious unexpected adverse events (AEs) considered related to either CORT125281 or enzalutamide and DLTs.

After all patients complete 3 cycles of treatment or discontinue treatment, the data will be unblinded and the DRC will meet to review the safety and available PK and PD data. The DRC will evaluate the frequency of DLTs, the DLT rate (the number of DLTs per week [7-day period] during the DLT-evaluation period), and overall tolerability in their assessment of the dose titration regimen as the Phase 2 RD. If the DLT rate for the regimen is $\geq 33\%$, alternative titration schemes may be considered as the regimen for the RD, such as greater time increments between dose escalations or limiting the upper range of the regimen to those dose levels corresponding to a DLT rate of $<33\%$. Once the DRC has determined the RD, patients assigned to Arm B who have not experienced dose reductions due to toxicity will have their CORT125281 dose escalated per the recommended Phase 2 regimen.

Phase 2a, Expansion Phase

Once the RD has been determined in the Dose-Determination Phase, the following cohorts will be enrolled and treated with CORT125281 + enzalutamide according to the RD regimen. The DRC may elect to expand more than 1 dose level, if needed, to better define the RD.

- **Abi-Resistant Cohort:** Patients who have progressed during treatment with abiraterone and have received no other AR-blocking therapies (N≈20)
 - **Food-Effect Subcohort:** The effect of food on the PK of CORT125281 will be evaluated in 10 patients enrolled to the Abi-Resistant Cohort. These 10 patients will have a 7-day Lead-In Period as follows:

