3.1.2 Expansion Phase (Phase 2a)

Once the RD has been determined in the Dose-Determination Phase, the following cohorts will be enrolled in the Expansion Phase and treated with CORT125281 + enzalutamide according to the RD regimen. The DRC may elect to expand more than 1 dose level, if needed, to better define the RD.

- Abi-Resistant Cohort: Patients who have progressed during treatment with abiraterone and no other AR-blocking therapies (N~20)
 - Food-Effect Subcohort: The effect of food on the PK of CORT125281 will be evaluated in 10 patients enrolled to the Abi-Resistant Cohort. These 10 patients will have a 7-day Lead-In Period as follows:

- Day -7: Single oral dose of CORT125281 administered under fasting conditions
- Day 1: Single oral dose of CORT125281 administered 30 minutes after a standard breakfast. These patients will initiate enzalutamide on Cycle 1 Day 2 to avoid confounding the assessment of the effect of food on CORT125281 PK

Patients in the Abi-Resistant Cohort who do not participate in the food-effect study will not have a Lead-In Period.

- ARant-Resistant Cohort: Patients who have progressed during treatment with enzalutamide or second-generation AR-blocking therapies (N≈20). Note: Patients in the ARant-Resistant Cohort will not have a Lead-In Period.

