9.4.2 Expansion Phase

Approximately 40 patients will be enrolled in the Expansion Phase.

- Twenty patients in the Abi-Resistant Cohort will ensure at least 80% power for detecting a doubling of the background rate of 23.5% in the PSA responder, defined as $\geq 50\%$ improvement in the PSA level from baseline. This calculation assumes 1-sided 0.1 significance level exact test of a single proportion against a fixed alternative. Under these assumptions, an absolute response rate of 40%, which represents a 59% improvement over the background rate, will support further evaluation of the regimen in the clinical program.
- Twenty patients in the ARant-Resistant Cohort will ensure at least 80% power for detecting an absolute improvement of 18% in the PSA responder rate over a rate of 8%, based upon the assumption that a response rate of 8% or less indicates no benefit. This calculation assumes 1-sided 0.1 significance level exact test of a single proportion against a fixed alternative. Under these assumptions, an absolute response rate of 20%, which represents an improvement of 12% over the background rate, will support further evaluation in the clinical program.

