2.4. Phase 2a, Expansion Phase

Once the RP2D has been determined in the Dose-Determination Phase, the following cohorts will be enrolled and treated with exicorilant + enzalutamide according to the RP2D regimen. The DRC may elect to expand more than 1 dose level, if needed, to better define the RP2D.

- **Abiraterone (Abi)-Resistant Cohort:** Patients who have progressed during treatment with abiraterone and have received no other AR-blocking therapies (N≈20)
 - **Food-Effect Subcohort:** The effect of food on the PK of exicorilant will be evaluated in 10 patients enrolled to the Abi-Resistant Cohort. These 10 patients will have a 7-day Lead-In Period as follows:
Day -7: Single oral dose of exicorilant administered under fasting conditions.
Day 1: Single oral dose of exicorilant administered 30 minutes after a standard breakfast. These patients will initiate enzalutamide on Cycle 1 Day 2 to avoid confounding the assessment of the effect of food on exicorilant PK.
Patients in the Abi-Resistant Cohort who do not participate in the food-effect study will not have a Lead-In Period.
- **AR Antagonist (ARant)-Resistant Cohort:** Patients who have progressed during treatment with enzalutamide or second-generation AR-blocking therapies (N≈20). Note: Patients in the ARant-Resistant Cohort will not have a Lead-In Period.

3. Study Objectives

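### The eligibility criteria for the Abi-Resistant Cohort do not enforce its own definition: some patients with a prior second-generation anti-androgen are admitted, and no rule says which Expansion cohort a patient resistant to both drug types enters.

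*Protocol*

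**What the plan says.** **Cohort definition.** The protocol synopsis describes the Abi-Resistant Cohort as "Patients who have progressed during treatment with abiraterone and have received no other AR-blocking therapies". Protocol 3.1 and 3.1.2 say the same in shorter form: "Patients who have progressed during treatment with abiraterone and no other AR-blocking therapies". SAP 2.4 repeats that these patients "have received no other AR-blocking therapies".

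**Criteria that sites apply.** Protocol 4.1, inclusion 6a, reads "Abi-Resistant Cohort: Patients must have progressed during treatment with abiraterone" and sets no limit on other AR-directed drugs. Protocol 4.2, exclusion 3, has two alternatives for this cohort. The first is prior enzalutamide ("Received prior therapy with enzalutamide or"). The second is "Received prior second-generation anti-androgen and require urgent disease response or stabilization". The synopsis carries the same pair. Inclusion 6b admits to the ARant-Resistant Cohort anyone who progressed on enzalutamide or a second-generation AR-blocking therapy, and does not mention prior abiraterone.

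**Benchmarks.** Protocol 9.4.2 and SAP Section 5 give each cohort 20 patients and a one-sided exact test at 0.1:
- Abi-Resistant: PSA response 23.5% against a doubling, with 40% supporting further evaluation.
- ARant-Resistant: 8% against an absolute gain of 18 points, with 20% supporting further evaluation. The 8% is "based upon the assumption that a response rate of 8% or less indicates no benefit".

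**The concern.** The second alternative in exclusion 3 has work to do only if patients who had such an agent but have no urgent need are let in. Under the definition, all of them would be out. No reading satisfies both texts, and Protocol Section 6 and 11.7 rule out waivers, so sites will follow Section 4.

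Two things are at stake. First, the Abi-Resistant Cohort can include patients outside the population to which its 23.5% and 40% figures are attached. Second, a patient who progressed on abiraterone and on a second-generation agent other than enzalutamide meets both 6a and 6b. The cohorts enroll in parallel (Protocol 1.5.1), the Expansion Phase has no allocation method (Protocol 5.11.1), and no order of precedence is stated. His cohort, and so the benchmark he counts toward, is undefined.

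**Working it through.** **Step 1. Who passes which text**

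| Patient, progressed on abiraterone | Cohort definition | 6a and exclusion 3 | 6b |
|---|---|---|---|
| No other AR-blocking therapy | in | in | no |
| Prior enzalutamide | out | out | only if he progressed on it |
| Other second-generation agent, urgent need | out | out | criterion met if he progressed, but the ARant list also excludes urgent need |
| Other second-generation agent, no urgent need, did not progress on it | out | **in** | no |
| Other second-generation agent, no urgent need, progressed on it | out | **in** | **yes** |

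The conflict is confined to the last two rows.

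**Step 2. Reproduce the plan's figures.** Inputs from Protocol 9.4.2: n = 20; Abi rates 0.235 and 2 × 0.235 = 0.47; ARant rates 0.08 and 0.08 + 0.18 = 0.26; one-sided 0.10. The rule is the smallest r with P(X ≥ r | 20, p0) ≤ 0.10.

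- Abi-Resistant: r = 7 gives 0.169 and r = 8 gives 0.0752, so r = 8 (40%). Power P(X ≥ 8 | 20, 0.47) = 0.802.
- ARant-Resistant: r = 3 gives 0.212 and r = 4 gives 0.0706, so r = 4 (20%). Power P(X ≥ 4 | 20, 0.26) = 0.804.

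Both stated designs reproduce. The Abi cohort clears 80% by only 0.002.

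**Step 3. Mixed cohort.** Let k of the 20 be in the last row of the table. Under the alternative, X = Bin(20 − k, 0.47) + Bin(k, 0.26). Under the null, X = Bin(20 − k, 0.235) + Bin(k, 0.08). The rule stays at X ≥ 8. The average null rate is [0.235(20 − k) + 0.08k]/20; at k = 4 this is (3.76 + 0.32)/20 = 0.204. The average alternative at k = 4 is (7.52 + 1.04)/20 = 0.428.

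| k (assumed) | Average null | Average alternative | P(go), null | Power |
|---|---|---|---|---|
| 0 | 0.235 | 0.470 | 0.075 | 0.802 |
| 1 | 0.227 | 0.460 | 0.063 | 0.776 |
| 2 | 0.220 | 0.449 | 0.052 | 0.747 |
| 4 | 0.204 | 0.428 | 0.034 | 0.683 |
| 6 | 0.189 | 0.407 | 0.021 | 0.612 |

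One such patient takes power below the promised 80%. The chance of a go under the null falls as well, so the test becomes more conservative.

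**The case against.** A reader might infer that the protocol itself assigns 8% to every patient let in by the gap. It does not. Exclusion 3 turns on having *received* a second-generation agent, while the 8% belongs to a cohort defined by *progression* on one. For patients who received such an agent without progressing on it, the documents give no PSA response rate. Enzalutamide, the drug named in the criterion, is barred outright, so the gap covers only other agents.

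A reader might also compute larger losses by holding the k patients at 8% while the rest respond at 47%. That supposes full effect in one group and none in the other. The protocol's own target for AR-antagonist-resistant patients is 26%, which is the matched assumption used above.

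A third tempting reading is that sites could steer patients toward the easier 20% threshold. Nothing in the documents suggests this, and a patient who progressed on both drug types fits the ARant definition anyway. What is missing is a rule.

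The remaining objections carry weight on severity. PSA response is a secondary endpoint, the primary objective is the MTD or recommended dose, Protocol 9.3 puts the emphasis on estimation, and the 40% figure is described as supporting further evaluation, not as a binding stop. Prior therapies and reasons for stopping them are collected (Protocol 6.2) and summarized with an anti-androgen category (SAP 8.4), so such patients would be visible. None of this removes the contradiction. Seeing these patients afterwards does not restore the sample size of a 20-patient cohort if they are set aside.

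**Conclusion.** The contradiction is certain; its numerical effect is conditional. The criteria admit patients whom the cohort definition excludes, and patients who progressed on both drug types qualify for two cohorts with no precedence rule. The sample-size arithmetic is sound for the cohort as defined.

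The size of the effect rests on two assumptions: k, which the documents do not give and which may be zero, and a 26% response among those k patients, taken from the ARant alternative. On those terms power drops from 0.802 to between 0.776 (k = 1) and 0.612 (k = 6). With the same patients at 8% under the null, the false-go probability falls, from 0.075 to 0.034 at k = 4. The risk in this cohort is therefore dropping an active regimen; type I error is not inflated. Severity is moderate because the endpoint is secondary and the threshold is a guide to further development.

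**What to change.** 1. Reconcile inclusion 6a and exclusion 3 for the Abi-Resistant Cohort (Protocol 4.1 and 4.2, and the synopsis copy) with the stated cohort definition, so that the criteria enforce it. Bring Protocol 1.5.1 into line too, since it describes the cohort by abiraterone progression alone.
2. Use one term for the barred therapies throughout. The definition says AR-blocking therapies without qualification, exclusion 3 speaks of second-generation anti-androgens, and 6b of second-generation AR-blocking therapies. Barring only second-generation agents would still leave the criteria narrower than the definition.
3. Add a sentence to 6a/6b assigning patients who progressed on both abiraterone and a second-generation AR antagonist to the ARant-Resistant Cohort only.
4. If the sponsor does intend to admit these patients to the Abi-Resistant Cohort, change the definition (including SAP 2.4) instead, and restate the background rate, threshold and power for that population.

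The change is best made before Expansion enrollment.

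Cost: a few lines of text, with no added patients, visits or procedures. Some patients move to the ARant-Resistant Cohort. A few who received such an agent without progressing on it become ineligible for both cohorts, because they fail the Abi definition and do not meet 6b. The sponsor should accept that loss knowingly.
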